The rooms will each consist of a portable tent with dimensions of at least 5x5ft base and height of 6ft. The critical requirement of said tent is sufficient thermal isolation from ambient temperatures to allow the maintenance of the required elevated or cooled temperature setpoints to within 1.8F. At present time, the most suitable tent is the THUNDERBAY Ice Cube 3 Man Portable Ice Shelter <https://www.amazon.com/gp/product/B019CU59VI>. This tent is surprisingly large, and has sufficient space to allow four adults to stand with 2 feet between adjacent people or two people with over 3 feet between them. The thermal radiant intensity of the walls of this tent do not match that of the elevated or cooled air temperature, because these walls directly contact and conduct to the ambient air and equilibrate between the ambient and internal temperatures, thus they radiate closer to the ambient temperature. Therefore, additional radiating membranes are used, consisting of sheets of fabric or paper hung from the ceiling or otherwise mounted with at least several inches displacement from the walls and having sufficient but low level of air flow to equilibrate the majority of the membrane to the internal air temperature. A GFCI-protected extension cord and powerstrip will be used to provide power to each tent.

The formula relied upon to obtain the ideal elevated temperatures is as follows, given as a lambda expression, which incorporates a first lambda (Python):

- $core2surf = \lambda core, air: core - (core-air)*0.191$

- $get_needed_room_air = \lambda air, febrile: core2surf(febrile, air) - ((98.6 - core2surf(febrile, air))/0.236)$

This gives us the needed heating temperature to get a desired change in body temperature, e.g. $get_needed_room_air(68, 100.4)$ returns 75.6F, meaning, in order to simulate a 100.4F core

temperature, a person must equilibrate to 75.6F air temperature before returning to receive a scan from the primary scanner located in 68F air temperature. This can be summarized more simply as, for every 1C (1.8F) elevation desired, the heated room must be that multiple of 4.23C (7.62F) above the scanning area's air temperature. Note, the exact coefficient was determined in a pilot study performed in June 2020, and may be refined by this study, which could alter the expected induced core temperatures.

Detailed Procedure - Blinded Temperature Study

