Each participant is given a random room letter provided by a display configured to output a letter randomly pulled from a uniform distribution of the room numbers A, B and C. The participant is to go to said room and locate the NFC scanner inside and scan their data collection form to obtain their **nfc-room-scan** (to be used in later identifying which temperature group their body is simulating). Once the participant has entered a room, the door to the room is closed and the participant is instructed to wait while remaining relatively still for ten minutes while avoiding touching their faces and avoiding stressful content (e.g. avoid browsing the internet). At the conclusion of the ten minutes, determined by study personnel, the door will be opened and the subjects will exit the room and walk to the scanning area to scan their data collection form to obtain their **nfc-temperature-scan** and receive three consecutive face scans. After these scans are complete, participants will proceed to additional thermographic face scanning equipment to receive additional scans within one minute of exiting the equilibration room. Study personnel will record the results of any additional equipment scans along with a unique number displayed on the primary thermographic system display at the conclusion of their primary temperature scan. Study personnel will then obtain an oral thermometry measurement. After all oral and IR thermometry measurements are complete, participants will proceed to the next blinded temperature room and the above process is repeated. This is repeated until all participants have received scans after spending ten minutes in all three blinded temperature rooms, at which point they proceed to one of the equilibration rooms, described below.

Detailed Procedure - Equilibration Study

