Each participant is directed to go to one of two rooms (labelled D or E, used for *heating* or *cooling*), enter as directed by a study personnel, scan their NFC sticker to enable their **nfc-equilibration-scan**, and subsequently sit in front of the primary thermographic system for 10 minutes. The subject may freely close their eyes and move around as long as their eye locations are visible by the camera system, which is aided by instructions provided by the operator to "ensure that at nearly all times you can see the lens of the thermal camera", with a picture as below posted nearby. At the conclusion of the serial measurement, study personnel will obtain an oral thermometry measurement. This process is repeated in the second room.

You may move around and close your eyes freely but please make sure both eyes are in view of the thermal image lens (see arrow) at all times.

Periodically check that you can see the entire ring (red circle) with both eyes.

Timing of Study Procedures

By appointing five rooms and interleaving equilibration times with scan times, it is possible to complete all measurements above on 9 subjects in 94 minutes, plus up to a 15-minute break in the middle of procedures. Briefly, every two minutes, one of the nine subjects is given a letter, whereupon they proceed to said lettered room to wait for 10 minutes to equilibrate for the blinded portion. The random letter drawing process is balanced so at most times, there are no more than 2 subjects in the room at a time. After the ten minutes is complete for a participant, study personnel will direct the participant to the scanning area. A third of the time, a new participant will be entering about the same time as a participant is leaving the room. The participant obtaining a scan will walk to the scan area, receive their primary scan, then any secondary scans, requiring a total of two minutes. Then the participant will receive a monitor-mode oral temperature, requiring up to two minutes. There will be approximately 4 minutes between this time and when the participant should go to the next lettered room for a ten minute equilibration time. This process repeats until all three rooms are complete, at which point the subjects are given an opportunity to have a break for up to 15 minutes. Note, we will interview subjects at the start of their break time and if they wish to begin sooner than 15 minutes and if the sequencing permits, the subject may proceed with less than a 15 minute break.

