In a second analysis, the equilibration time constants will be evaluated for possible linear correlations with the demographic data, although it is possible the small sample size and variability will preclude the detection of any significant correlations. In case there are nonlinear relations, scatter plots will be examined to determine if a low-order polynomial or other reasonable fit could explain a relation, while keeping in mind the fact each additional test is a multiple comparison, thus increasing the required p-value multiplicatively. Scatter-plots, trends and r-values will be reported, and this data may be collated with future collections of independent datasets.

The controlled face temperature data will be analyzed for sensitivity and specificity of each non-contact system used, first in a blinded analysis and then in an open-label analysis. First, the blinded face temperature data will be used to assign each recorded datapoint into normal, mild and moderate and severe fever groups, corresponding to below 38C (100.4F), 38-39C (100.4-102.2F), 39-40C (102.2-104F) and above 40C (104F). Note, the heated rooms' air temperatures were selected to produce simulated core temperatures that straddle the mild and moderate thresholds (hence, a well-performing system should place 50% of the measurements above the threshold and 50% below while a system relying on a bias-to-normal method might place only 10% above the selected threshold), therefore the severe fevers group

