should likewise have few subjects placed within it. The sensitivity and specificity for assessing each of a mild and a moderate fever temperature will be assessed in a straightforward manner by revealing the labels and determining the fractions of correctly- and incorrectly-labelled datasets. These labels are generated by first matching the NFC UUID associated with an *nfc-temperature-scan* to the previous closest in time *nfc-room-scan* of this same NFC UUID and taking that room's air temperature difference to the temperature scanner's air temperature and converting to simulated core body temperature. Next, this now open-label data will be used to determine the mean and standard deviation across the core temperature scans of each of these four groups. The standard deviation of oral temperatures below the 38C threshold will be used to determine the false positive rate, using an assumed normal distribution or a low-dimensional parametric fit to the actual oral distribution. A parametric fit to the distribution above 38C will be used to determine the sensitivity and specificity for mild, moderate and severe fever thresholds, corresponding to 38-39C, 39-40C and 40C and above, respectively, using the sum of the area under the curve above the appropriate threshold. The linear correlation between oral and imaging temperatures in the below-threshold range will be tested for significance. A subset of the data consisting of equal parts of over-threshold (fevers, by oral temperatures) and under-threshold participants will be tested for significance, and this significance level compared with that of the whole set.

In a second analysis, the controlled face temperature data will be analyzed for effect of confounds with the primary non-contact thermographic system. In this case, the physiologic correction parameters obtained from each individual will be examined for linear correlates or nonlinear relationships with the demographic data. As with the equilibration data, scatter-plots, trends and r-values will be reported, and this data may be collated with future collections of independent datasets.

Quality control and data management

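### The simulated-fever label has no time term and the primary system is always scanned first, so each system's sensitivity and specificity partly reflect scan timing

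*Combined protocol and SAP*

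**What the plan says.** **Label.** Section B, Controlled Temperature Rooms, derives the room temperatures from two static formulas. To simulate 100.4F, "a person must equilibrate to 75.6F air temperature before returning to receive a scan" in 68F air. The coefficient "may be refined by this study, which could alter the expected induced core temperatures". Section D assigns labels by taking the room's difference from the scanner's "air temperature and converting to simulated core body temperature". Elapsed time is not an input. The Appendix (Physiologic Model) bases the model on static equilibrium.

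**Order and delay.** The Blinded Temperature Study procedure puts three primary scans first: "After these scans are complete, participants will proceed to additional thermographic face scanning equipment to receive additional scans within one minute of exiting". Timing of Study Procedures gives the same order, but a different duration, with the walk included: "receive their primary scan, then any secondary scans, requiring a total of two minutes". No rotation of device order is described.

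**Timing records.** Participants scan their form on entering the room and again at the primary system. No exit time is mentioned. A secondary system without a logging mode gets a clipboard for its output and the primary's displayed number (Secondary Non-Contact Equipment). No time is mentioned there either.

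**Analysis.** Section D reports "sensitivity and specificity of each non-contact system used", obtained by revealing the labels and "determining the fractions of correctly- and incorrectly-labelled datasets". It notes that a good system should put half its readings above the threshold, while "a system relying on a bias-to-normal method might place only 10% above the selected threshold". The equilibration phase will estimate time constants for heating and cooling, but nothing feeds them into the labels.

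**The concern.** The label describes a face in equilibrium with the heated room. The scanned face has had 10 minutes to warm and has then been cooling in scan-area air. If warming is incomplete, every system is scored against an elevation that was not reached. If cooling is quick, the systems scanned later are scored against one that has partly gone.

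Because the primary is always first, device and delay cannot be separated. Two systems with the same response to the face would get different sensitivity and specificity from their place in the queue. Assessing real-world sensitivity and specificity is a stated goal of the study, so these are main outputs.

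**Working it through.** **Inputs from the documents.** Coefficients 0.191 and 0.236; rooms at 68, 75.6 and 83.2F with the scan area at 68F; 10 minutes per room; secondary scans within one minute of exit; primary scan set typically 10 s; core SD about 1F, observed SD 1.11F, physiologic SD 0.48F. Between rooms: 2 min of scans + up to 2 min oral + about 4 min waiting = 8 min.

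**Assumptions.** Tau (not given); primary scan 15 s after exit; mean core 98.6F; entry at scan-area equilibrium; label = own core + room elevation.

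**1. The plan's own figures.**
- Surface temperature for 100.4F in 68F air: 100.4 - 32.4 x 0.191 = 94.21F.
- Room needed: 94.21 - (98.6 - 94.21)/0.236 = 75.62F (plan: 75.6F). For 102.2F the result is 83.24F (plan: 83.2F).
- 0.191/(1 - 0.191) = 0.236, so the second coefficient is the algebraic inverse of the static model and makes no allowance for time.
- sqrt(1.11² - 1²) = 0.48F, as stated in Population Size.

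**2. Elevation at the scan.** With full-equilibrium elevation L (0, 1.8 and 3.6F for Rooms A, B and C), E(t) = L x (1 - exp(-10/tau_heat)) x exp(-t/tau_cool). With one tau for both directions:

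| tau (min) | reached in 10 min | E/L at 15 s | E/L at 1 min | Room B elevation, 15 s to 1 min |
|---|---|---|---|---|
| 2 | 99% | 0.88 | 0.60 | 1.58 to 1.08F |
| 5 | 86% | 0.82 | 0.71 | 1.48 to 1.27F |
| 10 | 63% | 0.62 | 0.57 | 1.11 to 1.03F |
| 20 | 39% | 0.39 | 0.37 | 0.70 to 0.67F |

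For heating tau 2-5 and cooling tau 2-8 min, E/L is 0.76-0.96 at 15 s and 0.52-0.88 at 1 min.

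**3. Share of Room B scans above 100.4F (benchmark 50%).** P(Z > 1.8(1 - E/L)/1.11). For a perfect device this is 35-48% at 15 s and 22-42% at 1 min over that grid, 27% and 24% at tau 10, and 16% and 15% at tau 20.

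**4. Sensitivity and specificity at 38C.** Core C ~ N(98.6, 1); reading = C + E(t) + N(0, 0.48); label = C + L; rooms equally weighted; all six room orders, with carry-over across the 8-minute gap.

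| Case | Sensitivity | Specificity |
|---|---|---|
| Label true | 92.9% | 92.9% |
| Grid, 15 s | 77.5-91.6% | 92.6-97.0% |
| Grid, 1 min | 51.8-86.7% | 94.4-98.1% |
| Change, 10 s later (grid) | -1.0 to -5.9 points | +0.3 to +1.0 |
| Change, 45 s later (grid) | -4.9 to -26.0 points | +1.1 to +2.5 |
| Change, 45 s later, tau 10 | -5.3 points (66.3 to 61.1%) | +0.4 |
| Change, 45 s later, tau 20 | -1.8 points (43.1 to 41.3%) | +0.2 |

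If the label is read instead as 98.6F + L, 45 s costs 4.8 to 22.7 sensitivity points on the grid and adds 1.7 to 5.4 specificity points.

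**5. What is fixed and what can reverse.**
- *Warm arrival.* Entry from an assumed 80F gives a starting elevation of 12 x 0.236 = 2.83F. With tau 5 and Room B first, elevation at exit is 1.8 + 1.03 x exp(-2) = 1.94F. It is 1.85F at 15 s, above the 1.8F label, and 1.59F at 1 min. The Room B share still falls by 9 points between those times.
- *Refitted coefficient.* A free-intercept refit to 10-minute endpoints at tau 5 lowers the label to 0.77 of its stated value, against a true 0.82 at 15 s and 0.71 at 1 min.
- *Device bias.* At tau 5, sensitivity + specificity - 1 falls from 0.79 at 15 s to 0.70 at 1 min for an unbiased device, but rises from 0.68 to 0.70 for one reading 1F high.

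**The case against.** The strongest reply is that the order effect may be small. Secondary systems stand next to the primary, whose scans typically take 10 s, and additional scans are limited to one minute after exit. The first secondary system may therefore follow by about 10 s, which costs about 6 points or less. A long tau shrinks the effect further. Both points stand, but neither removes the problem: later systems can approach the one-minute limit, and a long tau exchanges the order effect for incomplete equilibration on all systems.

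Several stronger readings are tempting, and the documents do not support them:
- *The plan's device comparison is invalid.* No formal between-device test is specified. The harm is to each system's reported figures and to any informal comparison.
- *The fixed order always favours the primary.* A device reading 1F high can score better when scanned later.
- *Readings always fall below the label.* Recruitment is in summer and no settling period is stated, although explanation and consent come before the rooms. A warm arrival or a refit could reverse the level. The ordering by delay after the heated rooms remains.
- *An honest late system will look biased to normal.* With SD 1.11F the one-minute shares are 22-42% on the grid and 15% at tau 20, against 10% in the design note. Shares near or below 10% appear only with the smaller 0.48F spread (for example 13.7% at tau 5 and 5.4% at tau 10).
- *Clipboard delays are lost.* They can be bounded from the linked primary scan and the one-minute limit, but not known exactly.
- *A loss smaller than the binomial standard error of one share is negligible.* The same participants are scanned on each system, so the differences are paired and that is the wrong yardstick.

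**Conclusion.** The label is wrong as written: it applies a static conversion to a face that may not have equilibrated and is cooling, although the study itself estimates the time constants involved. The fixed device order and incomplete time logging are a separate weakness with a cheap remedy. Together they mean that sensitivity and specificity partly measure timing, and that primary-secondary differences cannot be assigned to the device alone.

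The direction of the delay effect after Rooms B and C is secure as long as the face leaves the room warmer than scan-area equilibrium: a later scan sees a cooler face. The size is not secure. The range of about 5-26 sensitivity points for a 45 s delay rests on the assumed short time constants, the 15 s primary scan and entry at scan-area equilibrium. It is not a bound, since at tau 20 the loss is about 2 points. This should be fixed before data collection; confidence is medium because tau and the walk time are unknown.

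**What to change.** 1. Record the room exit time and the scan time on every device, including clipboard systems.
2. Rotate or randomise device order, and log the form ID at each device so that linkage does not depend on the primary's displayed number. If the order stays fixed, report sensitivity and specificity by time since exit and do not attribute primary-secondary differences to the device alone.
3. Keep the planned label. Beside it, as a pre-specified sensitivity analysis, report a label that follows elevation through the logged rooms: E_exit = L + (E_entry - L) x exp(-dwell/tau), then E(t) = E_exit x exp(-t/tau_cool). Use the heating tau if L exceeds E_entry and the cooling tau otherwise. Take the taus from the equilibration phase, freeze them before labels are revealed, and show a wide range of tau. State that they come from seated participants, the inner canthus and the primary camera, so they may not hold while walking or for forehead devices.
4. In that analysis, base any coefficient refit on the fitted asymptote, not the 10-minute endpoint.
5. Reconcile the one-minute and two-minute statements; the second may be a schedule slot.

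**Cost.** A little more logging and some analysis code. Rotation means that the primary is scanned later for some participants and takes the same delay penalty, so its results should also be reported by delay. Uncertainty in tau enters the adjusted label. The Appendix allows air conditions to change convective loss by a factor of two or more. If the true cooling tau is half the value used, true elevation at 1 min is 0.61-0.88 of the adjusted one (exp(-1/tau_cool) for tau_cool 2-8). That is why the adjusted label sits beside the planned one and does not replace it.

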The number of samples required to understand the impact of environmental or physiological confounds on surface temperature is dependent on the variability in the core-to-surface temperature physiologic offset. The variability in core body temperature has been found to be close to 1F but note the research design proposed here is not dependent on normal person-to-person variability in core temperature because the temperatures obtained are all referenced to each individual's core temperature. To estimate the likely physiologic variability in the population, we can extrapolate based on surface temperature data taken by the primary thermographic system obtained over the past six months because this should be approximately the vector sum of variability in core temperature, measurement accuracy, and the physiologic variability. This data must be interpreted with caution, because these have been obtained with less control over environmental conditions and furthermore we do not know the core body temperature variability in the preliminary data population, but it can provide a reasonable error bound. This data shows a standard deviation of 1.11F (note, this value is obtained without *any* bias-to-normal algorithm, which appears to be a novel feature in this research), which would suggest the physiologic variability component is at most 0.48F, or half a degree. Therefore, in order to determine the sensitivity and specificity at detecting elevated temperatures of 1.8F (100.4F threshold) to within 20% (meaning, can we significantly distinguish 100.40 from 100.04F with the aforementioned standard deviation in a one-sided paired t-test), we require 28 participants. To account for possible data collection failures, we intend to recruit as many as 45 participants.

Data Collection

- Demographic and clinical data: minimal demographic and clinical data will be collected by interview with the participant at the time of the imaging studies including age, gender, any disease- or autonomic-modulating treatment, height, weight and any antipyretic medications in past 12 hours in order to allow adjustment for confounding factors. We do not intend to collect data on menstrual cycle due to the additional potential privacy concerns this will place on participants worried about this data which is significantly more sensitive than other data being collected.

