Exclusion criteria

1. Contraindication to oral temperature measurement.
2. Inability to follow instructions.
3. Any diagnosis associated with abnormal core thermoregulation, e.g. autonomic dysfunction.
4. Obvious signs of tissue damage present in either inner canthus.
5. Facial artery abnormality if previously diagnosed.
6. Experienced discomfort while receiving most recent clinical oral thermometry measurement.

Study Procedures

After a detailed explanation of the study and its potential risks and benefits and informed consent will be obtained by the principal investigator or one of the co-investigators. Participants will then receive a single printed sheet containing places to enter the demographic and clinical information outlined above, as well as an NFC sticker uniquely linking the information on the sheet to all temperature measurements (Data Collection Sheet included in protocol materials).

The total time involved for participants will be approximately 120 minutes, with 100 minutes being spent in actual study procedures. The oral and thermal imaging evaluations will be performed in rooms identified as suitable for the purposes below. There are two separable phases to the study, the first (**blinded temperature phase**) involves isolated non-contact measurements and oral thermometry in a building-temperature room after spending ten minutes in each of three blinded elevated-temperature rooms and the second (**equilibration phase**) involves serial non-contact measurements of the inner canthi of seated participants over ten minutes and an oral thermometry measurement in one elevated temperature room and one reduced temperature room. All study procedures will be performed in groups sized no larger than allowed by St. Olaf College's COVID-19 restrictions on social distancing within the selected rooms. Participants will receive a \$20 gift card in compensation for their time and effort involved in participation in this study.

[figure not shown]
Oral Thermometry

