Once the break time is concluded for each subject, the process switches to the equilibration time measurement. Participants will wait an extra six minutes before proceeding to one of the rooms, in alternating order, so after ten minutes, the participant simply switches to the other equilibration room. A spreadsheet demonstrating the sequencing is included in the protocol materials, showing the time (10:00AM is selected as the start time for demonstrative purposes) in two-minute increments for 100 minutes, the participant (out of nine) who is currently switching rooms, the room they are being sent to (lettered A-E), which person is receiving the

thermographic scan, which person is receiving an oral measurement and the number of people at any given time in each room.

C. Safety

The risk to the participants participating in this study is low. Thermal imaging is a non-invasive, completely passive procedure. We do not expect any discomfort associated with thermal imaging. Oral thermometry is considered to have no risk, but it is possible participants could experience discomfort with oral thermometry. If participants indicate severe discomfort, the operator will immediately discontinue the procedure. The majority of the population has received a clinical oral thermometry procedure and participants are only eligible if they have received a clinical oral thermometry procedure in the past.

D. Analyses

It is foreseen that the two types of data will be analyzed separately and in two ways each. The equilibration data will be analyzed to determine the physiologic time constant in each dataset and grouped by direction of equilibration (heating, cooling). The groups of time constants will be assessed for significant differences between heating and cooling by two-sample t-test and a 95% confidence threshold. The average and standard deviation time constant (and if these are significantly different, this will be performed separately for heating and cooling) will be recorded and reported in an open-access publication with the rest of the results. The endpoint of each equilibration dataset will also be used to determine a linear physiologic offset (note, the existing parametric physiologic offset was previously determined in a 32-subject sample in June 2020 but for the purposes of this study, we intend to re-evaluate this equation) and the resulting equation and coefficients published along with the equilibration results.

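### Heating and cooling time constants come from the same participants but are compared with a test for independent groups, which probably costs power and can change what is published

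*Combined protocol and SAP*

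**What the plan says.** In the combined protocol and SAP, Section D (Analyses) derives a time constant from each equilibration dataset and groups the values by direction. It then states: "The groups of time constants will be assessed for significant differences between heating and cooling by two-sample t-test and a 95% confidence threshold". The result drives the reporting of the mean and SD: "if these are significantly different, this will be performed separately for heating and cooling".

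Section B shows that the two groups are the same people:

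- Study Procedures: the equilibration phase takes serial measurements "in one elevated temperature room and one reduced temperature room". Each participant's form carries "an NFC sticker uniquely linking the information on the sheet to all temperature measurements".
- Detailed Procedure - Equilibration Study: after the first room, "This process is repeated in the second room".
- Timing of Study Procedures: participants wait before "proceeding to one of the rooms, in alternating order, so after ten minutes, the participant simply switches to the other equilibration room".

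No section pairs the time constants by participant, and none includes a participant effect or room order in this comparison.

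**The concern.** A two-sample t-test treats the heating and cooling values as independent. Here each participant supplies one of each, and traits that make a person slow or fast to equilibrate may act in both rooms. The plan itself looks for correlations between the time constants and demographic data, which makes sense only if stable personal characteristics may matter. If they do, the two values from one person share them and tend to correlate positively. The test then uses too large a standard error for the difference.

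At stake is the pooled-or-separate rule. A real heating/cooling difference would more easily go undetected, and one blended mean and SD would be published as the physiologic time constant.

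Room order is also ignored. Target temperatures lie about 10F either side of the building setpoint (Controlled Temperature Rooms). The first room is therefore a step of roughly 10F, and the second, entered from the opposite room after an oral measurement, a step of up to roughly 20F. A purely first-order response would have the same time constant for both steps, so an order effect is possible, not established.

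**Working it through.** **Inputs from the documents.** Nominal level 5% (95% threshold, Section D). Sidedness is not stated; two-sided is assumed because the text speaks of differences between groups. n = 28 (required) and n = 45 (recruitment ceiling), both from Population Size.

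**Assumed inputs.** The documents give no SD, correlation, effect size or order effect for the time constants. I take equal SDs s, within-person correlation ρ from -0.3 to 0.7, a true difference of 0.5 SD, normality and complete pairs.

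**Step 1: level of the planned test.** With n pairs, the variance of the mean difference is 2s²(1-ρ)/n. The two-sample test uses 2s²/n. Its true two-sided size is therefore approximately

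2 × [1 - Φ(1.96/√(1-ρ))].

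At ρ = 0 this gives the plan's 5.0%. At ρ = 0.5, 1.96/√0.5 = 2.77, giving 0.6%. Simulation (40,000 trials per setting, n = 28) gives:

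| ρ | Two-sample type I error |
|---|---|
| -0.3 | 8.4% |
| 0 | 5.1% |
| 0.3 | 2.1% |
| 0.5 | 0.7% |
| 0.7 | 0.1% |

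A separate run of 200,000 trials per setting agrees and puts the paired t-test at 4.9% to 5.1% for every ρ from -0.5 to 0.9, at both sample sizes.

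**Step 2: power for a 0.5 SD difference, no order effect.** For the paired test the noncentrality is 0.5√n/√(2(1-ρ)). At n = 28 and ρ = 0.5 this is 0.5 × 5.29/1 = 2.65 on 27 df, giving 72.3%, in line with the simulation.

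| ρ | n = 28: two-sample / paired | n = 45: two-sample / paired |
|---|---|---|
| 0 | 45% / 44% | 65% / 64% |
| 0.3 | 44% / 58% | 67% / 79% |
| 0.5 | 43% / 72% | 70% / 91% |
| 0.7 | 42% / 91% | 75% / 99% |

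**Step 3: add an order effect.** A constant is added to the second room and the order alternates between participants (n = 28, difference 0.5 SD). The order-adjusted analysis uses within-person differences with a term for sequence (26 df).

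| Order effect | ρ | Two-sample / plain paired / order-adjusted power |
|---|---|---|
| 0.5 SD | 0 | 43% / 40% / 44% |
| 0.5 SD | 0.3 | 41% / 51% / 58% |
| 0.5 SD | 0.5 | 40% / 64% / 72% |
| 1 SD | 0 | 35% / 27% / 43% |
| 1 SD | 0.3 | 33% / 33% / 58% |
| 1 SD | 0.5 | 31% / 40% / 72% |

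Type I error of the order-adjusted analysis was 4.7% to 5.2% in every setting. The plain paired test becomes conservative when order matters: at ρ = 0 its size is 3.8% with a 0.5 SD order effect and 1.7% with 1 SD; at ρ = 0.5 it is 2.9% and 0.6%.

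**Step 4: incomplete pairs.** Population Size anticipates losses: "To account for possible data collection failures, we intend to recruit as many as 45 participants". If 10% of records failed independently (assumed), the number of 28 participants left with exactly one usable room would be 28 × 2 × 0.1 × 0.9 = 5.0.

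**The case against.** The strongest reply is that the error mostly runs in the safe direction and touches little. With positive correlation, false positives fall below 5%. Inflation needs a negative correlation, for which the documents give no basis. The comparison is not among the study's stated goals, carries no power claim and governs only how a time constant is reported. All of that stands, and it limits the weight of the point.

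Three further objections are partly right:

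- Saying that the level holds only at zero correlation is exact only without an order effect. At ρ = 0 the two-sample size is 4.3% with a 0.5 SD order effect and 2.8% with 1 SD; at ρ = -0.3 with 1 SD it is 5.4%. A balanced order effect makes the test more conservative still, so this refines the statement without rescuing the test.
- A plain paired t-test also misses 5% when order matters, and at ρ = 0.3 with a 1 SD order effect it has no more power than the planned test. This is why order belongs in the model.
- Population Size sizes the study "in a one-sided paired t-test", but for a different question, so it does not prove an inconsistency. It shows only that the authors distinguish the two tests. The pairing follows from the procedures alone.

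Finally, the size of the loss is unknown: at n = 28 the gain from pairing ranges from nothing at ρ = 0 to 49 points (91% - 42%) at ρ = 0.7.

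**Conclusion.** The concern holds. The planned test assumes independent groups, and the design gives two values per participant, linked by one identifier. The probable consequence is lost power, not excess false positives: at n = 28, 43% against 72% for an assumed 0.5 SD difference and an assumed correlation of 0.5. No loss arises if the correlation is zero and order has no effect. A negative correlation would reverse the problem. The figures rest on assumed correlation, effect size and order effect, equal variances, normality and complete pairs.

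The test should be changed before analysis, but the damage is confined to the pooled-or-separate reporting rule. The requirement of 28 participants, the physiologic offset and the sensitivity and specificity analyses do not depend on it.

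**What to change.** In Section D, replace the two-sample t-test with a within-participant analysis and state that it is two-sided. Preferred is a linear mixed model for the time constant with participant as random effect and direction and room order as fixed effects. It uses the linkage already collected, allows for the alternating order and keeps participants with one usable room. A paired t-test on heating minus cooling is simpler but not equivalent: it ignores order and drops incomplete pairs.

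Report the mean heating-minus-cooling difference with its 95% CI. Give the mean and SD for each direction beside any pooled value, so that the publication does not turn on one p-value.

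The cost is one or two sentences and slightly more analysis work, with no new data. Degrees of freedom at n = 28 fall from 54 (two-sample) to 27 (paired) or 26 (order-adjusted on complete pairs), which costs about 1 percentage point of power at zero correlation. The order adjustment also assumes that order shifts heating and cooling values equally. The order-adjusted figures above come from complete-pair differences; the mixed model itself was not simulated, so its gain from keeping incomplete pairs is not quantified.
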